Social Support and Stress Reduction for Caregivers of Young Adults With IDD **Study Protocol**

NCT Number: NCT05938998 Unique Protocol Id: STUDY00149679

Version date: 6/21/2023

Principal Investigator: [name]

University of Kansas Medical Center RESEARCH PROTOCOL INVOLVING HUMAN SUBJECTS

Version date: 6/21/2023

Principal Investigator: [name]

Study Title: Social Support and Stress Reduction for Caregivers of Young Adults with IDD

Co-Investigator(s): [name], [name]

I. Purpose, Background and Rationale

1. Aim and Hypotheses

Being a caregiver to an individual with intellectual and developmental disabilities (IDD) can be stressful and may result in adverse health effects for the caregiver. Additionally, caregivers of individuals with IDD must navigate new support systems when the young adult with IDD reaches a transitional age and loses school-based supports. In conjunction with the *Chef BoyID* study (IRB # 148424), we propose a 12-week study which will consist of 12 group-based sessions offered to the caregivers of transitional age individuals with IDD, some of whom may be enrolled in the *Chef BoyID* study. These sessions will cover 1 hour of social support and resource provision, and 1 hour of stress reduction through yoga to help with the transition.

- 1. Evaluate factors impacting the feasibility of recruitment, retention, assessment, and satisfaction of a caregiver intervention providing social support and stress reduction.
- 2. Measure changes in psychosocial health (i.e., stress, social support, family empowerment), physiologic stress (salivary cortisol) and lifestyle health behaviors (i.e., physical activity, sleep) of caregivers participating in the intervention.
- 3. Assess impact of caregiver participation in the intervention on health behaviors of the young adult with IDD (i.e., physical activity, diet, sleep).
 - a. Hypothesis 1: Young adults in Chef BoyID who have a caregiver partake in the intervention will have improved Chef BoyID outcomes compared to young adults in Chef BoyID who do not have a caregiver participating in the intervention.
 - b. Hypothesis 2: Reduction in stress of caregivers improves caregiver health behaviors & dependent health behaviors.

A. Background and Significance

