children with disabilities compared with family caregivers for children without disabilities (Bodde et al., 2022; Gallagher & Hannigan, 2015; Lee et al., 2017). Previous research implementing yoga or mind-body interventions have documented reductions in psychologic and physiologic stress and reductions in stress symptoms(Chong et al., 2011; Park et al., 2021; Pascoe et al., 2017). Because the physical and mental health of caregivers is associated with the health and wellbeing of their child with a disability (Murphy et al., 2007), it is important to assess interventions aimed at reducing stress and providing support for parents during these transition years.

B. Rationale

Interventions focusing on providing resources, social support and mind body activities may help to reduce caregiver stress and improve their health behaviors (e.g., sleep and activity), and collectively, this may also result in improvements in the health behaviors of their young adult with IDD, some of whom may be participating in a concurrent physical activity and cooking skills intervention (see [name] study: The promotion of healthy lifestyles for young adults with intellectual disabilities, referred to as "Chef BoyID", IRB #148424).

II. Research Plan and Design

A. Study Objectives

The purpose of this study is to examine the feasibility and initial efficacy of a social support, resources, and stress reduction intervention for the promotion of healthy lifestyle behaviors and the reduction of caregiver stress and strain.

B. Study Type and Design

This is a single arm longitudinal trial. We will recruit up to 40 caregivers of young adults with IDD. Some caregivers will be recruited as their young adult is participating in the Chef BoyID intervention, and some will be recruited for a cohort at Down Syndrome Innovations, unrelated to Chef BoyID participation. This is a 12-week social support, resources, and stress reduction intervention delivered in person to a group of caregivers of young adults with IDD of transitioning age at the Center for Children's Healthy Lifestyles and Nutrition, Down Innovations orat the University of Kansas Energy Balance Laboratory location. Participants will be asked to attend one 2 hour group session each week. All sessions will have a 1-hour discussion on resources and social support and 1-hour of yoga. All yoga sessions will be taught by 200 RYT certified instructors. Outcome assessments will be collected at baseline and after the 12-week intervention.

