C. Subject Criteria

Inclusion: 1) caregiver of a young adult with IDD 2) self-reported ability to participate in a yoga class with no contraindications to participation. *Exclusion*: 1) Actively participating in another health lifestyles interventional research study.

D. Specific methods and techniques used throughout the study

1. Intervention:

- **a.** *In person, small group instruction:* Participants will attend weekly two-hour small group instruction sessions at the Center for Children's Healthy Lifestyles and Nutrition, Down Syndrome Innovations, or the University of Kansas Energy Balance Laboratory location. All sessions will have a 1-hour discussion on resources and social support and 1-hour of yoga.
 - i. Discussion on resources and social support (1 hour): This session will consist of a brief presentation of resources to aid in the transition process for the young adult with IDD. In the first session, caregivers will be asked to provide topics of specific interest and sessions will be customized to their expressed needs. Examples of topics covered include: transportation, employment options, group home options, navigating

- Medicaid waiver, respite care options, health, etc. Time will be provided for caregivers to connect with each other, ask questions, and share their own resources and experiences. A discussion guide will be provided for each week.
- ii. Yoga class (1 hour): Each yoga class will be taught by a certified yoga instructor ([name] or [name]). The session will include breathing / warm up (~5minutes), asanas/poses (~45min) and savasana/meditation (~10min).

2. Schedule of Evaluations

Assessment	Screenin g Visit: (Day-30 to Day - 1)	Baseline: KUMC Visit 1 (Day -14 to Day -1)	KUMC Visit 2 (Week 12- Week 14)	Weekly	Monthly
Informed Consent Form	Х				
Demographics	Х				
Enrollment		Х			
Anthropometrics		Х	Х		
Session Attendance				Х	
Physical Activity – Accelerometer		Х	X		
Caregiver strain		Х	Х		
Perceived Stress Scale		Х	X		
Physiologic Stress (Cortisol)		х	X		
Social support		Х	Х		
Family Empowerment		Х	Х		
Sleep		Х	X		
Satisfaction (semi- structured interview)			Х		
Adverse Events		Х	Х	Х	Х

3. Description of Evaluations

- **A.** Caregiver demographics: contact information, age, gender, relationship to person with IDD, income, education level, number of children, employment status, race, ethnicity (Hispanic/not Hispanic)

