Caregivers of young adults with IDD in the ChefBoyID study will be recruited and informed about the caregiver portion of the study when their young adult is recruited/consented to participate to the ChefBoyID study. Caregivers may also be recruited through informational flyers distributed through Down Syndrome Innovations' email list and quarterly promotion materials. Flyers and emails will be modified to reflect the addition of the caregiver portion of the intervention.

Interested caregivers will be asked to contact the study coordinator via email, our website or a dedicated study phone number that will be included in all recruitment materials. The study coordinator will contact the interested individuals by phone to answer questions and conduct an initial eligibility screening. Zoom meetings will be scheduled with those who remain interested and potentially eligible to complete the exercise screening session and to obtain informed consent.

B. Screening Interview/Questionnaire:

Caregivers with a young adult with IDD who are interested in participating in the social support, resource, and stress reduction intervention will be contacted to by the research team. Researchers will go over the eligibility criteria, and if eligible, review the study and the informed consent.

C. Informed Consent Process And Timing Of Obtaining Of Consent

Remote video chat sessions (Zoom) will be scheduled with participants who are deemed to be initially eligible to participate. This video chat session will provide an opportunity to describe the project in detail, answer questions, verify eligibility, and to obtain consent immediately following the consent/assent of the participant with IDD (For the ChefBoyID study, if applicable). Prior to the consenting session, the participant will be sent the consent form and cover letter through The University of Kansas Medical Center's (KUMC) secure email system. The study team will use the "share screen" option on Zoom to walk through each section of the consent document while noting questions that arise and answering these questions fully. Participants who are willing to participate in the study will sign and date the consent and/or assent forms electronically via REDCap. The study team member who conducted the consent meeting will also sign and date after reviewing the signed consent forms and verifying completeness. Study staff will provide the participant with a fully signed consent form for their records.

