V. Data Analysis and Reporting

A. Statistical and Data Analysis

To determine the feasibility of social support, resource, and stress reduction sessions, we will calculate the mean number of sessions attended, and the percent of participants who attended ≥ 75% of the scheduled sessions. Chi-Square or t-tests will be used to compare baseline characteristics (age, sex, BMI, PA, income, other demographic characteristics) between participants who attended ≥ 75% vs. <75% of sessions. To assess changes in physical activity, social support, family empowerment, stress, caregiver strain, and sleep across the intervention, we will compare baseline and 12-week assessments using a t-test or non-parametric equivalent for paired samples, and we will determine effect size using Cohen's D. Per Aim 3, Hypothesis A of the caregiver intervention, we will compare outcomes of participants with IDD (cooking skills, fitness, weight, dietary intake, physical activity) between participants who had a caregiver participate and those who did not using independent samples t-tests. Per Aim 3, Hypothesis B, we will analyze correlations between change in caregiver stress (perceived stress scale; cortisol; caregiver strain) and caregiver health behaviors (physical activity, sleep) and dependent health behaviors (cooking skills, fitness, weight, dietary intake, physical activity). Finally, we will complete a qualitative analysis of the semi-structured interviews to gain insight on the acceptability and satisfaction with the program.

B. Outcome

We expect to know the feasibility and acceptability of the social support, resources, and stress reduction program for caregivers and determine if we should apply for external funding to complete and adequately powered trial.

C. Study results to participants

Study results will not be sent to the participants.

D. Publication Plan

The research results will be presented at a conference and published in a peer-reviewed journal upon completion of the pilot study.

VI. References

- Bodde, A. E., Helsel, B. C., Hastert, M., Suire, K. B., Washburn, R. A., Donnelly, J. E., & Ptomey, L. T. (2022). The Prevalence of Obesity and Lifestyle Behaviors of Parents of Youth with Intellectual and Developmental Disabilities. *Disability and Health Journal*, 101430. https://doi.org/https://doi.org/10.1016/j.dhjo.2022.101430

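### Aim 3 Hypothesis A compares self-selected groups of young adults by unadjusted t-tests, with no stated use of baseline, and its aim is worded as impact

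*Combined protocol and SAP*

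**What the plan says.** Section I.1 states Aim 3 as: "Assess impact of caregiver participation in the intervention on health behaviors of the young adult with IDD". Its first hypothesis, which V.A calls Hypothesis A, is that young adults in Chef BoyID with a participating caregiver "will have improved Chef BoyID outcomes compared to young adults in Chef BoyID who do not have a caregiver participating in the intervention".

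Section V.A lists five outcomes for this hypothesis (cooking skills, fitness, weight, dietary intake, physical activity) and compares them "between participants who had a caregiver participate and those who did not using independent samples t-tests". It names no covariate, time point or change score. For the caregivers' own outcomes the same paragraph is explicit: "we will compare baseline and 12-week assessments using a t-test or non-parametric equivalent for paired samples". The only baseline comparison planned is between caregivers who attended at least 75% of sessions and those who attended fewer.

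Section II.B describes a single-arm study of up to 40 caregivers, of whom "some will be recruited for a cohort at Down Syndrome Innovations, unrelated to Chef BoyID participation". Entry is voluntary. Under III.A, "Interested caregivers will be asked to contact the study coordinator via email, our website or a dedicated study phone number". Under II.C a caregiver needs "self-reported ability to participate in a yoga class with no contraindications to participation" and must not be active in another healthy-lifestyle intervention study.

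**The concern.** Whether a young adult has a participating caregiver depends on the family's interest and on the caregiver's eligibility, not on allocation. The two groups may therefore differ before the intervention starts. An unadjusted t-test on follow-up values cannot separate such a gap from an effect of the caregiver programme. A t-test on change scores makes a different assumption about how the gap would evolve. The plan does not say which is meant, and no table would show how far apart the groups were at the start.

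At stake is the reading of Aim 3. A difference that was already present at baseline, or that reflects which families come forward, could be described as an impact of the programme when the results are published (V.D).

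**Working it through.** **Figure to reproduce.** There is none. The documents give no alpha, power, effect size, SD or group sizes for Hypothesis A. The ceiling of 40 counts caregivers, some of them unrelated to Chef BoyID.

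**Assumptions (not from the documents).** 20 v 20 young adults; two-sided 5% test; no true effect; outcome SD 1; baseline gap d; pre-post correlation rho of 0.5 or 0.8.

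**Model.** Baseline B ~ N(d·g, 1), with g = 1 if the caregiver takes part. Follow-up Y = rho·B + u·g + sqrt(1 - rho²)·e. The term u is any group difference at follow-up that baseline does not explain.

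**Bias.** Follow-up levels: rho·d + u. Change score: u - (1 - rho)·d. Baseline-adjusted difference (ANCOVA): u.

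**Standard error.** With f = sqrt(1/20 + 1/20) = 0.316, it is f for levels, f·sqrt(2(1 - rho)) for change and, with no gap, f·sqrt(1 - rho²) for ANCOVA.

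**Case 1: baseline is the only confounder (u = 0).** The false-positive rate is the rejection probability of a noncentral t with 38 degrees of freedom and noncentrality bias/SE.

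- Levels, d = 0.5: bias 0.5 × 0.5 = 0.25 or 0.8 × 0.5 = 0.40; noncentrality 0.25/0.316 = 0.79 or 0.40/0.316 = 1.26; rejection 12.0% or 23.4%.
- Levels, d = 0.2: bias 0.10 or 0.16; rejection 6.1% or 7.8%.
- Change, d = 0.5: bias -0.25 or -0.10; rejection 12.0% or 7.8%.
- ANCOVA: bias 0; rejection 5%.

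Reversing the sign of d reverses the sign of each bias and leaves the two-sided rates unchanged. At 10 v 10 with d = 0.2, the levels test rejects about 5.5-6%.

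**Does one baseline-using estimate win in general?** Biases at 20 v 20, for rho 0.5 / 0.8:

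| Case | Levels | Change | ANCOVA |
|---|---|---|---|
| d = +0.5, u = 0 | +0.25 / +0.40 | -0.25 / -0.10 | 0 / 0 |
| d = +0.5, gap persists, u = (1 - rho)·d | +0.50 / +0.50 | 0 / 0 | +0.25 / +0.10 |
| d = +0.5, motivation adds u = 0.2 | +0.45 / +0.60 | -0.05 / +0.10 | +0.20 / +0.20 |
| d = -0.5, motivation adds u = 0.2 | -0.05 / -0.20 | +0.45 / +0.30 | +0.20 / +0.20 |

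In the persisting-gap row the levels test rejects 34% of the time, the change test 5% and ANCOVA 14% / 8%. The ordering of change and ANCOVA depends on whether the gap persists and which group starts higher. In the last row the levels test is the least biased or ties with ANCOVA in size, but only because two errors offset. Simulation with 40,000 runs per scenario agrees with these figures.

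**The case against.** **The details may sit elsewhere.** The endpoints are Chef BoyID outcomes. That study has its own protocol, which is not among these documents, and the schedule in II.D.2 does not collect these outcomes for the young adult. Time points and baselines may be defined there. This stands as a limit: the omission is shown for this protocol only. But this protocol owns the hypothesis and its test, and for this comparison it points to no definition in the other.

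**Improvement suggests change.** The hypothesis speaks of improved outcomes, and an independent t-test on change scores fits V.A. This also stands in part. The wording leans towards change without settling it, and V.A is explicit about baseline only for the caregivers' own outcomes.

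**The problem is small and exploratory.** With a 0.2 SD gap the inflation is slight. V.A itself says only that outcomes will be compared, and V.B sets the expected result as "We expect to know the feasibility and acceptability of the social support, resources, and stress reduction program for caregivers", with an adequately powered trial as a later step. This fixes the severity as modest. It does not remove the point, because initial efficacy is part of the purpose in II.A and Hypothesis A has its own planned test.

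**A reader might infer that levels and change would give contradictory conclusions.** In case 1 the two estimates do differ in sign in 33-62% of simulated data sets over gaps of 0 to 0.5 SD. The lower part of that range (33-40%) arises with no gap at all, as noise around zero. Both tests are significant with opposite signs in under 1% of data sets. At least one is significant, with signs opposed, in about 1-17%. The sign figure should not be used as a headline.

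**Conclusion.** The concern holds at modest size. As written, Hypothesis A compares self-selected groups without adjustment, leaves the use of baseline unstated, plans no baseline table for those groups, and sits under an aim worded as impact. If follow-up levels are tested, a 0.5 SD gap in either direction gives 12-23% false positives instead of 5%, and a 0.2 SD gap gives 6-8%. These rates rest on the assumed 20 v 20, correlation of 0.5 to 0.8, no true effect and no other confounder.

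Three stronger readings are not supported. The documents do not show that a baseline gap exists or which way it runs. They do not show that ANCOVA or change scores would generally be the less biased, and neither removes unmeasured confounding such as family motivation. Nor is the feasibility assessment compromised: attendance and acceptability do not depend on this comparison.

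**What to change.** In V.A:

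- Name the time point for Hypothesis A.
- Where Chef BoyID holds a baseline, replace the unadjusted comparison of levels with the baseline-adjusted (ANCOVA) difference and its 95% CI. Show the change-score difference with its 95% CI beside it as a sensitivity estimate.
- Name the main estimate before the Chef BoyID data are linked. State that the two rest on different untestable assumptions: ANCOVA that baseline is the only confounder, change that the gap would otherwise have persisted.
- Tabulate the young adults' and families' baseline characteristics by caregiver participation, with participation defined by enrolment.
- Report the result as an exploratory association between self-selected groups, and align the wording of Aim 3 in I.1.
- Report any outcome without a Chef BoyID baseline descriptively, and say why.

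The cost is a few sentences, one table, a second estimate per outcome and one degree of freedom per ANCOVA model. It also requires confirming that linked Chef BoyID baselines exist for the five outcomes and for families whose caregiver did not join, and checking what the Chef BoyID protocol already defines.
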